4 STUDY DESIGN

4.1 OVERALL DESIGN

This is randomized, sham-controlled, patient-masked, outcome assessor-blinded, prospective, multi-center study designed to support a *de novo* submission and FDA clearance for the Phagenesis Phagenyx® System for treatment of oropharyngeal dysphagia following a stroke. The study will follow an adaptive group sequential design with unblinded sample size re-assessment. To ensure 180 evaluable patients with 7-day data and assuming a 20% dropout rate, 225 patients will be enrolled initially. An interim analysis for futility will occur after the first 60 patients complete their 7-day visit and another interim analysis will be performed for efficacy after 120 patients complete their 7-day visit. The total sample size may be increased up to 338 patients after the second interim analysis to ensure 270 evaluable patients. Up to 15 investigational centers across the US and Europe will participate in this study. The enrollment period is expected to be approximately 24 months and patient participation will last for approximately 11 weeks. Patients will be assessed at the following intervals: baseline.

CONFIDENTIAL Page 32 of 71

within 48 hours of treatment, 7 days, 14 days or at discharge, whichever is first, and 11 weeks after completion of study treatments.

Investigational sites will be chosen from centers that have standardized protocols for treating patients with dysphagia post-stroke. Centers will be selected so that US sites represent the majority, with the ability to contribute at least 60% of the total patients. All sites must have speech language therapists/pathologists (SLT/SLP) on staff as well as affiliated VFSS facilities and personnel.

All enrolled patients will have the Phagenyx® Catheter placed and will receive either an active treatment with Pharyngeal Electrical Stimulation or a sham treatment by a HCP who is un-blinded to the treatment assignment.

Randomization will use stratification based on site and baseline PAS. Minimization may also be included to ensure group balance for study site and additional baseline covariates.

Administration of all protocol-specific assessments, other than PES or sham treatments, will be conducted by personnel who are blinded to the treatment assignment, including speech pathologists providing standard dysphagia care (excluding VitalStim and e-Stim). The standard dysphagia care data will be collected on the eCRF.

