5.2 EXCLUSION CRITERIA

An individual who meets any of the following criteria will be excluded from participation in this study:

- 1. Brainstem stroke.
- 2. Evidence of traumatic brain injury or subarachnoid hemorrhage.
- 3. Other, non-cerebrovascular, structural brain diseases, including multiple sclerosis or other demyelinating diseases, brain tumors (other than small meningioma), neurodegenerative diseases (including Alzheimer and Parkinson disease), hydrocephalus, and leukodystrophy
- 4. Dysphagia from conditions other than stroke.
- 5. Pre-stroke history of swallowing complaints or treatment or history of diseases known to be associated with swallowing problems (other neurological, head and neck cancer.
- 6. Distorted oropharyngeal anatomy (e.g., pharyngeal pouch, major pharyngeal surgery or head /neck surgery)
- 7. Currently being treatment for pneumonia.
- 8. Mute, global aphasia; no usable speech or auditory comprehension (scores 3 on NIHSS question 9, Best Language)
- 9. NIHSS score of 25
- 10. Presence of a tracheostomy
- 11. Any active implanted device (e.g., cochlear implant, ICD, permanent pacemaker)

CONFIDENTIAL Page 35 of 71

- 12. Any progressive neurological disorder (e.g., Parkinson's Disease, Multiple Sclerosis)
- 13. Cognitive impairment that prevents compliance with protocol-specific instructions and assessments
- 14. Unstable cardiopulmonary condition, i.e., not on maintenance therapy.
- 15. Currently participating in another investigational study
- 16. Pregnant or planning to become pregnant while participating in the clinical study
- 17. Known Allergy to oral radiographic contrast media (specifically barium)
- 18. Any other condition in the opinion of the investigator will prohibit the patient from participation and follow up.

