5.4 STRATEGIES FOR RECRUITMENT AND RETENTION

Patients will be screened and recruited by the investigators and/or coordinators at each site. Eligible patients could be in an inpatient rehabilitation center, having been transferred from the acute care facility in which they had been initially treated for the stroke, or site standard unit for post-acute stroke patients. The length of stay for these patients should be for up to 2 weeks to complete the study requirements for treatment and 14 day (+/- 1 day) follow up.

Stroke patients identified as dysphagic by clinical bedside assessments between the ages of 18 and 90 years, will be screened for study enrollment. The patient or their legal guardian will be eligible to sign the ICF after the study team explains the study and the patient and family have time to read and understand as well as ask all questions. The importance of study compliance will be emphasized throughout the informed consent process.

The length of study participation is approximately 11 weeks, including post treatment follow-up visits at 48 hours (+/- 24 hrs), 7 days (+/- 1 day), 14 days (+/- 1 day) or discharge, whichever is first, and 11 weeks (+/- 1 week).

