Patients will be masked to treatment and will not be told if they receive the active or Some patients randomized to active treatment will have some sham treatment. sensation associated with the pharyngeal stimulation; however, a few with higher sensory thresholds may not feel anything as demonstrated in prior studies. The patients randomized to the sham treatment will not receive any actual stimulation and thus should not have any sensory feeling associated with the sham treatment. The informed consent documentation will advise that the patient "may or may not" feel the pharyngeal stimulation, so that those patients receiving either the active PES treatment of the sham treatment will not necessarily expect to feel anything. All procedural steps will be carried out in a very similar manner for both groups of patients. The only difference in the administration of the two treatments is that no electrical stimulation will be administered during the sham treatment. The way the treatment is administered will not give the patient any idea as to their treatment as there are no light or sound indicators associated with the administration of PES. Moreover, the individual administering treatment will be facing the patient at all times during the delivery of electrical (or sham) stimulations, and the base station will be facing the treatment administrator. The shape of the base station will prevent the patient from seeing what is on the administrator's screen during treatment delivery. The active/sham treatments will also be administered in privacy so that no other study personnel or patient caregivers/family members can observe the treatment or treatment assignment.

For those patients randomized to the sham group, a different Base Station will be used that delivers no electrical current and does not have the ability to treat with PES. This Base Station will have only "demo" software loaded, so the unblinded healthcare professional administering the treatment will have a screen and the ability to adjust the settings, without any changes or current begin delivered.

An assessment of whether the patient remains blinded will be included at the 14-day (+/- 1 day) or discharge whichever is first, follow-up assessment. This will be done via a question to the patient asking them if they believe they received the active or sham treatment and their response will be documented on the eCRF.

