8.1.4 BARTHEL INDEX

The Barthel Index is a widely-used measure of functional disability and a measurement of quality of life, as it measures the extent to which someone can function independently and has mobility in their activities of daily living (ADL) i.e., feeding, bathing, grooming, dressing, bowel control, bladder control, toileting, chair transfer, ambulation and stair climbing. It was developed for use in rehabilitation patients with stroke and other neuromuscular or musculoskeletal disorders. The BI is completed by the patient on the

CONFIDENTIAL Page 46 of 71

provided worksheet and the data are entered on the eCRF. It is completed at the baseline, 14-day, and 11-week visits. Details regarding the administration of the BI can be found in the eTMF.

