8.1.5 MODIFIED RANKIN SCALE (mRS)

The mRS is a single-item, global outcomes rating scale for patients who are post-stroke. It is used to categorize level of functional independence with reference to pre-stroke activities rather than on the observed performance of a specific task.

The mRS is used to measure the degree of disability in patients who have had a stroke, as follows:

- 0: No symptoms at all
- 1: No significant disability despite symptoms; able to carry out all usual duties and activities
- 2: Slight disability; unable to carry out all previous activities, but able to look after own affairs without assistance
- 3: Moderate disability; requiring some help, but able to walk without assistance
- 4: Moderately severe disability; unable to walk without assistance and unable to attend to own bodily needs without assistance
- 5: Severe disability; bedridden, incontinent and requiring constant nursing care and attention
- 6: Dead

The mRS is administered by qualified and trained study staff. It is completed at the baseline, 14-day, and 11-week visits and the data will be entered on the eCRF. Details regarding the administration of the mRS can be found in the eTMF.

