4.3.8. Missing, Unused, and Spurious Data

In general, there will be no substitutions made to accommodate missing data points. All data recorded on the CRF will be included in data listings that will accompany the clinical study report.

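### The Barthel Index, an exploratory endpoint, is completed by the patient, although entry admits some patients who may be unable to complete a form and whose masking can be breached by sensation; blinded trained staff should score it

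*Protocol*

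**What the plan says.** - **Who rates the Barthel Index (BI).** Protocol 8.1.4: "The BI is completed by the patient on the" worksheet provided, and the data are then entered on the eCRF. The visits are baseline, day 14 (or discharge, in the schedule of activities) and week 11. The section adds: "Details regarding the administration of the BI can be found in the eTMF".
- **Who does the other assessments.** Protocol 4.1: "Administration of all protocol-specific assessments, other than PES or sham treatments, will be conducted by personnel who are blinded to the treatment assignment". For the next instrument, 8.1.5 says: "The mRS is administered by qualified and trained study staff". The FOIS (8.1.7) can be completed by clinicians from charts, journals and patient reports, with family or other sources used for verification.
- **Who can enter.** Inclusion criterion 3 accepts 0 or 1 on NIHSS item 1a. Exclusion criterion 8 removes mute or globally aphasic patients, described as "no usable speech or auditory comprehension (scores 3 on NIHSS question 9, Best Language"); lower non-zero language scores are not excluded. Exclusion criterion 13 removes patients whose cognitive impairment stops them complying with instructions and assessments.
- **Patient masking.** Protocol 6.3: "The patients randomized to the sham treatment will not receive any actual stimulation and thus should not have any sensory feeling" from the sham procedure. The same paragraph expects only a few actively treated patients to feel nothing.
- **Analysis.** The BI is listed among the exploratory general stroke health outcomes (Protocol 3; SAP 4.8). SAP 4.3.8 says that in general "there will be no substitutions made to accommodate missing data points". For continuous exploratory endpoints, SAP 4.8 describes an ANCOVA that includes the baseline value.

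**The concern.** A form that the patient must complete is a fragile way to measure disability in this population. A drowsy patient, or one with marked but not global aphasia, may not manage it. The protocol text says nothing about help, interview or a proxy. If such forms are left blank, the BI is compared in a less disabled subset than was randomised.

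The second issue is the source of the rating. Stimulation is set from each patient's own detection and tolerance levels (6.1.3), so most actively treated patients are expected to feel something, and sham patients should feel nothing. The patient is therefore the least securely masked source for a functional score. Trained staff already score the mRS at the same visits, and under 4.1 they are blinded.

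At stake is the interpretability of one exploratory outcome at day 14 or discharge and at week 11. No confirmatory conclusion depends on it.

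**Working it through.** The documents state no BI effect size, standard deviation, missing-data rate or power, so there is no BI figure to reproduce. The check is a comparison of sections, followed by an illustration on assumed rates.

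**1. Could an eligible patient be unable to complete the form?**

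| Rule | Effect |
|---|---|
| Inclusion 3 | admits item 1a = 1 |
| Exclusion 8 | removes only a language score of 3 |
| Exclusion 13 | removes cognitive impairment that prevents compliance; does not name aphasia or inability to write |
| Inclusion 6 | requires the individual to be able to consent; removes some of those who could not complete a form |

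So some such patients can be randomised. The exposed group is reduced by exclusion 13 and inclusion 6, but not shown to be empty. Its size cannot be derived from the documents.

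**2. What would lost scores do?**

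The protocol's own enrolment figures are consistent: 180 / 0.8 = 225, and 270 / 0.8 = 337.5, rounded up to 338. I take the 180 evaluable patients as a reference denominator only, because it is defined by 7-day data and not by BI data at day 14 or week 11. Let m be the assumed share lost.

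- Patients left: N = 180 × (1 − m)
- Standard error relative to no loss: √(180 / N)
- Detectable difference in SD units (1:1 allocation, one-sided 0.025, 80% power): (1.960 + 0.842) × √(2 / (N/2))

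| m (assumed) | N | SE ratio | Detectable difference (SD) |
|---|---|---|---|
| 0% | 180 | 1.000 | 0.42 |
| 10% | 162 | 1.054 | 0.44 |
| 20% | 144 | 1.118 | 0.47 |
| 30% | 126 | 1.195 | 0.50 |
| 40% | 108 | 1.291 | 0.54 |

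The loss of precision is modest over the whole range.

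**3. Does it bias the comparison between arms?**

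A missing baseline form precedes treatment, so treatment cannot cause it. Loss driven by severity and similar in both arms narrows the population and costs precision; it does not by itself bias the arm difference. Bias from missing data would need losses at follow-up that differ by arm.

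Self-rating is a different matter. If patients who believe they were treated rate themselves b points better, the arm difference shifts by about b × (share believing active in the active arm − share believing active in the sham arm). The documents give neither b nor the shares. Protocol 6.3 makes a positive difference in shares plausible. The baseline score is unaffected, so this concerns only day 14 or discharge and week 11.

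**4. Is another route available?**

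The schedule of activities puts the BI, mRS and NIHSS at the same three visits. Staff scoring therefore adds no visit. Protocol 7.2 already calls for telephone contact at week 11 and for retrieving records of patients discharged to inpatient care elsewhere; a staff-scored BI could use both.

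**The case against.** The other side has real force.

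- **The eTMF may settle it.** 8.1.4 refers to it for BI administration, and assisted or proxy completion may be described there. This stands as a limit on what can be said. But 8.1.5 also refers to the eTMF for the mRS and still names who administers it. If the eTMF made staff the raters of the BI, 8.1.4 would need correcting anyway.
- **4.1 is not flatly contradicted.** A reader might infer that it is. Blinded staff can hand over a worksheet that the patient then completes, and the EQ-VAS (8.1.9) is also marked by the patient. The contrast with the mRS shows a better method to hand, not a contradiction.
- **Guardian consent is not a settled entry rule.** A reader might take "The patient or their legal guardian will be eligible to sign the ICF" (5.4) as proof that patients unable to act for themselves are enrolled. Section 10.1.2 also allows a representative, where permitted. But inclusion criterion 6 and the Statement of Compliance require the patient's own consent. That is a separate inconsistency to reconcile, and this point does not rest on it.
- **The SAP does not commit to an ANCOVA of the BI.** It does not name the BI as continuous, and says exploratory endpoints may be modelled. Only if the BI is analysed that way does a patient without a baseline form drop out despite having later scores.
- **The items are concrete.** Stairs, transfers and continence leave less room for optimism than a global rating, and 6.3 sets out masking measures and a blinding question. This limits the likely size of self-rating bias; it does not remove the possibility.
- **The BI is exploratory**, and the staff-administered mRS covers disability at the same visits. This is correct and sets the weight of the point.

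**Conclusion.** The point holds as a low-cost improvement to an exploratory endpoint. The protocol text names the patient as the only source of the BI, admits some patients who may be unable to complete a form, and expects sensation to differ between arms. Scoring by blinded trained staff is a better method and is already in place for the mRS.

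The size is unknown. The 10% to 30% loss is an assumption; on it, the standard error rises by about 5% to 20%. The likely effect of lost scores is a narrower population and less precision.

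A reader might go further and infer that scores will go missing in the most disabled, that the comparison is confined to fitter patients, or that optimism passes straight into the arm difference. The documents do not establish any of these: there is no missing-data rate, exclusion 13 and inclusion 6 remove some of the patients concerned, the eTMF instructions are unseen, and the effect of sensation on self-rating is not quantified. The primary and secondary tests, the sample size and the interim decisions are untouched.

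**What to change.** In Protocol 8.1.4, replace completion by the patient with wording to this effect:

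> Trained study staff blinded to treatment assignment score the BI at the same visits as the mRS. They use observation or clinical records where available, and otherwise interview the patient or a caregiver, by telephone if necessary at week 11. The source of information is recorded at each visit and kept the same where feasible.

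Bring the BI instructions in the eTMF into line with this.

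**Cost.** A protocol wording change and a few minutes of staff time at visits where staff already score the mRS. No added visit or assessor is needed.

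**Limits.** Interview-based scores still depend on a patient or caregiver who may have guessed the arm, so the masking concern is reduced and not removed. An identical source at every visit will not always be possible, since patients move from inpatient care to home or another institution by week 11. Recording the source at least lets the analysis show how scores were obtained in each arm.

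Separately, reconcile the consent provisions in 5.4 and 10.1.2 with inclusion criterion 6 and the Statement of Compliance.

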8.1.5 MODIFIED RANKIN SCALE (mRS)

The mRS is a single-item, global outcomes rating scale for patients who are post-stroke. It is used to categorize level of functional independence with reference to pre-stroke activities rather than on the observed performance of a specific task.

The mRS is used to measure the degree of disability in patients who have had a stroke, as follows:

- 0: No symptoms at all
- 1: No significant disability despite symptoms; able to carry out all usual duties and activities
- 2: Slight disability; unable to carry out all previous activities, but able to look after own affairs without assistance
- 3: Moderate disability; requiring some help, but able to walk without assistance
- 4: Moderately severe disability; unable to walk without assistance and unable to attend to own bodily needs without assistance
- 5: Severe disability; bedridden, incontinent and requiring constant nursing care and attention
- 6: Dead

The mRS is administered by qualified and trained study staff. It is completed at the baseline, 14-day, and 11-week visits and the data will be entered on the eCRF. Details regarding the administration of the mRS can be found in the eTMF.

8.1.6 NIH STROKE SCALE (NIHSS)

The NIH Stroke Scale is a widely-used tool that was built to assess the cognitive effects of a stroke. In more scientific terms, it provides a quantitative measure of stroke-related neurologic deficit. Although the NIHSS was first developed as a clinical tool for research on stroke patients, it is now used by health professionals to determine the severity of a stroke. It also helps create a common language between all people involved in a stroke patient's treatment. In a treatment setting, the scale has three major purposes:

- It evaluates the severity of the stroke
- It helps to determine the appropriate treatment
- It predicts patient outcomes

It is completed at the baseline, 14-day, and 11-week visits and the data will be entered on the eCRF. Details for the NHISS can be found in the eTMF.

CONFIDENTIAL Page 47 of 71

8.1.7 FUNCTIONAL ORAL INTAKE SCALE (FOIS)

The FOIS was developed to document the functional level of oral intake of food and liquid in stroke patients with dysphagia³⁰. It is a 7-point ordinal scale that can easily completed by clinicians based on information contained in medical charts, dietary journals, and/or patient reports. Verification of patient reports may be obtained by a spouse or family members or from a variety of sources for institutionalized patients. The FOIS shows strong criterion validity and cross-validation compared with standard clinical measures of stroke outcome. The FOIS has demonstrated sensitivity in expected increase in functional oral intake over a 6-month recovery period in stroke patients. It is completed at the baseline, 7 day, 14-day, and 11-week visits and the data will be entered on the eCRF. Details regarding the administration of the FOIS can be found in the eTMF.

Functional Oral Intake Scale

Level	Description		
1	Nothing by mouth (NPO)		
2	Tube dependent with minimal attempts of food or liquid		
3	Tube dependent with consistent intake of liquid or food		
4	Total oral diet of a single consistency		
5	Total oral diet with multiple consistencies but requiring special preparation or compensations.		
6	Total oral diet with multiple consistencies without special preparation, but with specific food limitations.		
7	Total oral diet with no restriction.		

8.1.8 DYSPHAGIA SEVERITY RATING SCALE (DSRS)

The DSRS is composed of a 3-component score¹⁹ that includes feeding independence, but nutrition level and diet modification is split into the components of liquid feeding and overall diet consistency. The DSRS is the sum of the scores of each of the 3 individual components rather than a combination of the three components into an ordinal scale. Moreover, the DSRS scoring is not based on underlying physiology as the DOSS attempts by use of the VFSS, but instead captures only the result of the swallowing dysfunction as does the FOIS. The DSRS has not been formally validated, but it may provide more sensitive or specific information than the FOIS with its 13-point scale. The DSRS has been used in prior studies that have assessed PES, and is thus being used for this study. It is completed at the baseline, 7 day, 14-day, and 11-week visits and the data will be entered on the eCRF. Details regarding the administration of the DSRS can be found in the eTMF.

Dysphagia Severity Rating Scale

Fluids	Score	Diet	Score	Supervision	Score
No oral fluids	4	Non-oral feeding	4	No oral feeding	4

CONFIDENTIAL Page 48 of 71

Pudding consistency	3	Puree	3	Therapeutic feeding (SLP/trained staff)	3
Custard consistency	2	Soft, moist diet	2	Feeding by 3 rd party (untrained)	2
Syrup consistency	1	Selected textures	1	Eating with supervision	1
Normal fluids	0	Normal	0	Eating independently	0

Notably, the DSRS was developed in Europe where nomenclature for fluid consistency differs from that used in the US. Hence, in order to standardize the DSRS with the modified barium swallow protocol adopted for the MBS/VFSS, the following interpretation will be used:

Normal fluids = Thin Liquid Syrup consistency = Nectar Custard = Honey

